9.3 POPULATIONS FOR ANALYSES

Given that the intervention being tested requires parent adherence to recommendations to achieve success, we will use an intention-to-treat analysis approach.

While we anticipate that the intervention and control groups will be similar due to random assignment, we will adjust for any variables in our analysis that are not equal between the groups given the small sample size. In addition, we will analyze for any effect of primary home language on the study outcomes, as this may affect families' ability to navigate systems of care in the U.S.

9.4 STATISTICAL ANALYSES

9.4.1 GENERAL APPROACH

This section outlines the statistical analysis strategy and procedures for the study. We plan to use the primary outcome data to assess the RE-PACT intervention's feasibility, acceptability, and fidelity. We anticipate being underpowered to assess efficacy using the clinical endpoints of the intervention in this pilot study. The clinical outcome endpoints will be used to develop an estimate of effect size. Categorical variables will be displayed as percentages, and continuous variables as means with standard deviations (if normally distributed) or medians with IQR (if skewed). For inferential statistics, two-sided p-values <0.05 will be considered statistically significant. A detailed Statistical Analysis Plan (SAP) describing all details of the analyses has been developed and will be finalized prior to the database lock and the analysis of the final study data.

9.4.2 ANALYSIS OF THE PRIMARY ENDPOINT(S)

RE-PACT's primary outcomes will be analyzed descriptively, and will evaluate feasibility, acceptability, and fidelity. We will assess the outcomes against our pre-specified measures of success, e.g., achieving at least 80% enrollment. We will evaluate the actual vs expected performance of each intervention component (mHealth texting surveillance, action planning, just-in-time adaptive coaching intervention response) and completeness of each data collection element in intervention and active control groups. We will also determine overall positive, neutral, and negative reports of feasibility and acceptability using content analysis of qualitative data, similar to our previous intervention feedback research. We will explore any patterns if / when challenges emerge, e.g., enrollment refusal or drop out, low reported use of the intervention activities.

9.4.3 ANALYSIS OF THE SECONDARY ENDPOINT(S)

Clinical Outcomes. We will test differences between treatment (intervention or control) groups in the primary and secondary respiratory illness outcomes. Our goal with these analyses is to estimate effect sizes for the differences between groups which will allow precise sample size calculations for a future large-scale trial.

Primary clinical outcome is the severe respiratory illness rate, defined as the total number of severe respiratory illnesses divided by the person-months over the 6-month follow-up period. The severe respiratory illness rate will be analyzed using a negative binomial (NB) regression model to account for overdispersion in the count data. For the primary analysis, univariate NB regression analysis will be conducted with study arm as a predictor variable. Study site will be included as a stratification factor in the primary analysis to account for stratified randomization. The observed effect size of the analysis will be quantified in terms of relative risk (RR) and reported along with the corresponding 95% confidence interval.

As a secondary analysis, multivariate NB regression analysis will be performed to compare the severe respiratory illness rates between study arms. In this analysis, clinical and demographic characteristics will be included as covariates in an initial non-parsimonious model. The least absolute shrinkage and selection operator (lasso) and elastic net penalty methods for negative binomial regression models will be utilized to identify a parsimonious model with independent covariates. These methods are considered state-of-the art techniques for variable selection (Wang Z., et al. Stat Methods Med Res. 2016).

Longitudinal changes in the severe respiratory illnesses within and between study arms, will be evaluated with generalized linear mixed effects model with a logit link function and subject specific random effects. An autoregressive (AR) correlation structure will be utilized to account for within subject correlations. In this analysis, the presence/absence of severe respiratory illness at the monthly assessments will be the dependent variable, study arm will be included as a predictor variable and study site as a stratification variable to account for the stratified randomization.

Secondary clinical outcomes include total hospital days during severe respiratory illness, numbers of systemic steroid courses, systemic antibiotic courses, respiratory ED visits and death. The numbers of systemic steroid courses, systemic antibiotic courses, and respiratory ED visits over the 6 months follow-up period will be analyzed using NB regression analyses in a similar fashion as described above for the primary outcome. Observed effect sizes will be reported along with the corresponding 95% confidence intervals. The presence/absence of systemic steroid courses, systemic antibiotic courses, and respiratory ED visits will be documented at the monthly assessments and longitudinal changes within and between study arms will be analyzed using generalized linear mixed effects modeling with a logit link function and patient specific random effects. The total number of hospital days over the 6 months follow-up period will be analyzed using analysis of variance (ANOVA) with study site as stratification factor. In a secondary analysis, analysis of covariance (ANCOVA) will be performed where clinical and demographic baseline characteristic will be included as covariates and the lasso method will be used to identify a parsimonious

model. Longitudinal changes in the number of hospital days per hospitalization will be analyzed using a normal mixture linear mixed effects model with patient specific random effects. The normal mixture component will be included in the model to capture the probabilities of a hospitalization at the monthly follow-up. Parameter estimation will be performed using the Expectation-Maximization algorithm which is the standard method for parameter estimation of mixture models.

Missing values, e.g., due to loss of follow-up, missing monthly visits, will be evaluated by conducting a sensitivity analysis comparing the results obtained from the complete case analysis to the results obtained by imputation-based analyses. Specifically, multiple imputation (MI) will be used to impute missing values of primary and secondary clinical outcomes. For monotonic missing values data structures, we will use regression-based MI techniques. For non-monotonic missing value data structure, on the other hand, we will use Markov Chain Monte Carlo based imputation techniques.

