Preventing Respiratory Illness in Severe CP Requires Broad, Adaptive, Timely Intervention. Action planning and health coaching are effective strategies in other populations. For example, from 2003 to 2013, hospitalization rates for pediatric asthma dropped by half (from 9.6% to 4.7%), during which time asthma action plan use increased significantly.⁴² A family intervention linking home-based asthma coaching to action planning significantly reduced hospitalizations in poorly controlled asthma.⁴³ However, respiratory illness in severe CP has broad comorbid triggers, e.g., emesis, dysphagia, aspiration, seizures, among others. Simple action plans or coaching alone cannot address the breadth of respiratory illness triggers or potential responses. For example, if a parent of a child with severe CP follows an action plan directed towards bronchospasm, it would not effectively address an acute infectious lower respiratory infection. Parents of children with severe CP need action plans and coaching, but they also need an efficient direct extension to their clinical team for adaptive, just-in-time clinical response directed specifically to real-time acute problems.

The Plans for Action and Care Transitions (PACT) intervention was developed by this team to prevent hospitalizations for children with complex chronic diseases including severe CP. After integrating systematic literature review,⁴⁴ parent interviews,³⁸ and a national expert panel,³⁹ each focused on preventing hospitalization, PACT was designed to leverage evidence-based strategies from different populations: asthma action planning,⁴⁵⁻⁴⁷ health coaching,⁴⁸⁻⁵⁰ and feedback at our Parent Advisory Group's monthly meetings. PACT delivered action planning and coaching activities to children with diverse complex diseases, including severe CP, and a PACT RCT found 40% lower hospitalization rates for intervention vs control patients.¹⁸

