4.2 SCIENTIFIC RATIONALE FOR STUDY DESIGN

Rational for the study design. Conducting this pilot study will provide a high degree of certainty that the final RE-PACT protocol is feasible, acceptable and can be delivered with fidelity. This is a critical approach to designing interventions that can be integrated in diverse, real-world, settings and sustained.

Using an RCT design (i.e., with a control group who do not receive intervention) is necessary to establish effect sizes needed to adequately power an efficacy trial. The findings from this study will allow precise estimation of effect sizes to conduct a fully powered, multisite hybrid Type 2 effectiveness-implementation RCT.

Rationale for the type and selection of control conditions. The control group will be randomly assigned, allowing the study team to conclude that endpoint differences between each group are most likely due to the intervention itself.

Potential problems associated with the control group. The control group may have pre-existing respiratory action plans created during routine clinical care. In addition, the coach may have difficulty avoiding contaminating the control group by inadvertently conducting coaching activities to those not assigned to the intervention group. This risk will be minimized since action plans using the study protocol will only happen for intervention subjects, and coaching is triggered only through mHealth text responses and texting will only be set up for those assigned to the intervention.

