9.2 SAMPLE SIZE DETERMINATION

We will enroll a total of 90 participants. Wave 1 will contain 10 participants (5 UW, 5 UCLA); Wave 2 will contain 20 participants (10 UW, 10 UCLA); Wave 3 will contain 60 participants (30 UW, 30 UCLA). Based on this team's preliminary work, eligible children average one severe respiratory illness per year and we estimate 50% of participants will experience at least one respiratory illness during the period of enrollment. We expect to be able to maintain contact and collect data from ≥90% of the participants at the final follow-up, evenly divided between intervention and control groups. We assume this sample will not be powered to establish the efficacy of the intervention; however, it will provide a sufficient sample to determine feasibility and estimate effect sizes which will be used for power calculations in the future large RCT. The following table shows the attainable power levels for detecting various differences in severe respiratory illness rates (primary clinical outcome) between study arms at the two-sided 0.05 significance level, based on a NB regression model with an overdispersion parameter of $\phi=1.0$.

Attainable power levels for detecting differences in severe respiratory illness rates between arms at the two-sided 0.05 significance level based on a NB regression model, assuming a sample size of 45 subjects per arm with a missing value rate of 10% or less.

Relative Risk (RR)	Number of severe respiratory illnesses in intervention arm over 6-month Follow-up period				
	5	10	15	20	25

(Control vs. Intervention) ($\lambda=0.02$)*	($\lambda=0.40$)*	($\lambda=0.06$)*	($\lambda=0.08$)*	($\lambda=0.10$)*
3.0	19%	29%	38%	45%
4.0	31%	41%	59%	68%
5.0	42%	62%	74%	83%

*Severe respiratory illness rate per patient-month

Hence, large effect sizes with RRs ranging between 3.0-5.0 for comparing the severe respiratory illness rates between study arms will be detected with 19-88% power at the two-sided 0.05 significance level.

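### Sections 4.2 and 9.4.3 promise precise effect sizes for planning the next trial, but on the plan's own inputs the 95% CI for the rate ratio spans about 2.1- to 2.3-fold either way

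*Combined protocol and SAP*

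**What the plan says.** The only secondary objective (section 3) is to establish the effect size of RE-PACT. Three places say what the estimate will deliver:

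- Section 9.4.3: the goal is to "estimate effect sizes for the differences between groups which will allow precise sample size calculations for a future large-scale trial".
- Section 4.2: "The findings from this study will allow precise estimation of effect sizes to conduct a fully powered, multisite hybrid Type 2 effectiveness-implementation RCT".
- Section 9.2: the sample is sufficient to "estimate effect sizes which will be used for power calculations in the future large RCT".

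Section 9.4.3 also says that the RR will be "reported along with the corresponding 95% confidence interval". No section gives an expected interval width, a precision target, or a rule for carrying the uncertainty of the estimate into the next sample size.

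Sections 4.1, 5.5, 9.2 and 9.4.1 state that the pilot is not powered for efficacy. Sections 2.2 and 4.1 use more modest language and describe the effect sizes as likely or preliminary.

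**The concern.** Power and interval width come from the same standard error. A design that cannot reliably distinguish a moderate effect from none cannot estimate that effect precisely either, so the concession on power and the claim of precision conflict. A reader is told that the test is weak but that the estimate can be relied on for planning.

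What is at stake is the sample size of the next trial. Required n varies with the inverse square of the log RR, so an imprecise RR entered as the design effect gives an unstable n. If the pilot happens to overstate the effect, the efficacy trial will be underpowered.

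**Working it through.** **Inputs**

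- Analysable children: section 9.2, "assuming a sample size of 45 subjects per arm with a missing value rate of 10% or less". 45 × 0.9 = 40.5, taken as n = 40 per arm.
- Control mean: one severe illness per year (9.2) over 6 months gives μc = 0.5 per child.
- Overdispersion: φ = 1.0 (9.2).
- True RR, intervention versus control: an assumption. I use 0.6, because section 2.2 reports that "a PACT RCT found 40% lower hospitalization rates for intervention vs control patients", and 1.0 as the no-effect case.

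**1. The plan's own figure.** The document gives no interval width. Its nearest figure is power: RRs of 3.0 to 5.0 (control versus intervention) "will be detected with 19-88% power at the two-sided 0.05 significance level". With a pooled-null variance, n = 40 and φ = 1, I match 12 of the 13 legible cells within 2 points, but only if the monthly rate is used as the mean over one month of follow-up. At the stated 6 months no variant tried reproduces the table; the same formula gives about 57% to nearly 100%. That is a separate matter, and nothing below uses the table. Note that a 40% reduction is 1/0.6 = 1.67 on the table's scale, well below its smallest row.

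**2. Expected precision.** For a negative binomial log RR with equal follow-up:

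SE = √[(1/μc + 1/μi + 2φ)/n], and the 95% CI factor is exp(1.96 × SE).

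| True RR | Illnesses | SE | CI factor | 95% CI |
|---|---|---|---|---|
| 0.6 (μi = 0.3) | 40 × 0.8 = 32 | √[(2 + 3.333 + 2)/40] = 0.428 | 2.31 | 0.26 to 1.39 |
| 1.0 (μi = 0.5) | 40 × 1.0 = 40 | √[(2 + 2 + 2)/40] = 0.387 | 2.14 | 0.47 to 2.14 |

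Power at RR 0.6 from the same SE: 0.511/0.428 − 1.96 = −0.77, which is 22%.

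**3. Sensitivity of the CI factor (RR 0.6 and 1.0)**

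- 40.5 per arm: 2.30 and 2.13. All 45 per arm retained: 2.21 and 2.05.
- Section 9.2 also expects 50% of participants to have at least one respiratory illness. If that means severe illness, and is applied to the control arm, μc is 0.69 (Poisson: 1 − e^−μ = 0.5) to 1.0 (negative binomial, φ = 1: 1 − 1/(1 + μ) = 0.5). With φ = 1 and 40.5 per arm the factor is about 1.85 to 2.11.
- φ from 0 to 2 with μc = 0.5 and 40.5 per arm: 1.85 to 2.56.
- For comparison, a factor of 1.5 needs about 141 (RR 1.0) to 172 (RR 0.6) analysable children per arm.

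**4. Consequence for the next trial.** For a like-for-like 6-month trial at 80% power:

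n per arm = (1.96 + 0.842)² × (1/μc + 1/μi + 2φ)/(ln RR)² = 7.85 × 7.333/0.261 ≈ 221 at RR 0.6.

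This n is halved if the pilot RR is about 0.46 and doubled if it is about 0.71. I simulated 20,000 pilots (40 per arm, means 0.5 and 0.3, φ = 1) and sized the next trial on each pilot's point RR, holding μc and φ at their true values:

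- about 29% give less than half the needed n;
- about 13% show an RR of 1 or more, from which no trial of benefit can be sized;
- about 64% are off by more than twofold in either direction, counting the RR ≥ 1 pilots as off.

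A normal approximation with SE 0.428 gives 27%, 12% and 63%. As an illustration, at the approximate lower-quartile pilot RR of 0.45 the n would be about 105 per arm, with true power about 49%.

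**The case against.** The case for the plan is substantial. It says repeatedly that it is underpowered, calls its effect sizes preliminary in places, and commits to reporting the RR with a 95% CI. Effect size is the secondary objective, and the primary endpoints are descriptive. The next trial's protocol is not written, and its designers may well look at the whole interval. The RR of 0.6 is borrowed from a trial that section 2.1 describes as reducing all-cause hospitalization in children with complex diseases, not respiratory admissions in severe cerebral palsy. The 50% figure in 9.2 allows a somewhat narrower interval.

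Most of this limits the consequences but does not rescue the word at issue. No reading in step 3 brings the CI factor below about 1.8. Reporting an interval does not make it narrow, and nothing says that the interval will be used in sizing.

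Some stronger readings are tempting and are not supported:

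- That the next trial will be badly mis-sized. This follows only if the point RR is used as the design effect and the true RR is near 0.6.
- That an effective intervention would be dropped. No go/no-go rule uses the clinical RR. Adjustments between waves rest on feasibility, acceptability and fidelity (8.1, 9.4.6), and section 10.1.6 sets no predefined stopping points.
- That the plan hides its size. It does not.
- That a meaningful upper percentile can be given for the resulting n. It depends on how pilots with an RR of 1 or more are handled, so none is given here.

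Whether to label results at p < 0.05 is a reporting preference and not part of this point.

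**Conclusion.** The claim of precision in 4.2 and 9.4.3 is wrong as written. Expected precision is a factor of about 2.1 to 2.3 either way on the one-illness-per-year input, and about 1.85 to 2.1 on the more favourable 50% reading. The interval widths rest on the plan's sample size, retention, follow-up and overdispersion. The sizing consequence additionally assumes a true RR of 0.6 and use of the pilot point estimate. Under those conditions a mis-sizing of more than twofold is more likely than not. The fault is an unsupported description, together with no safeguard on how the RR is used; it is not concealment and not a flaw in the pilot's primary purpose. Severity: should-fix.

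**What to change.** In 4.2 and 9.4.3, delete the word precise and state the expected width: a 95% CI factor of about 2.1 to 2.3, for example roughly 0.26 to 1.39 if the true RR is 0.6, with the inputs listed.

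In 9.2 and 9.4.3, state that:

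- the pilot RR will be reported with its 95% CI and will not be used as the design effect;
- the future trial will be sized on a pre-stated clinically relevant RR;
- the pilot will inform the control-arm rate, overdispersion and retention, each carried forward with its uncertainty.

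The cost is a few sentences and a less favourable stated property. No patients, data collection or analyses are added.

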1.2 SCHEMA

1.3 SCHEDULE OF ACTIVITIES

	STUDY PERIOD							
	Enroll- ment Visit	REPACT Intervention Period						Final Visit
Personnel involved	Research Coordina- tor	Clinicians						Research Coordina- tor
Month	0	1	2	3	4	5	6	End of Month 6
Timepoint	T ₀	T ₁	T ₂	T ₃	T ₄	T ₅	T ₆	T ₇
Confirm eligibility	X							
Informed Consent	X							
Baseline Assessment	X							
6-month Assessment								X
Randomization	X							
Subject Payment	X							X
Usual comprehensive medical care and coordination via Complex Care Program		X	X	X	X	X	X	
Intervention Arm Only								
Text Msg Training	X							
Weekly mHealth text message and response		X	X	X	X	X	X	
Intervention overview		X						
Create action plan		X						
Action planning		X	X	X	X	X	X	
JIT coaching		X	X	X	X	X	X	
Monthly study assessments		X	X	X	X	X	X	

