5.5 STRATEGIES FOR RECRUITMENT AND RETENTION

Recruitment

We will recruit caregivers of children with severe CP between 0-17 years old. We will recruit a total of n=90 participants (n=45 at each site) divided across 3 waves. In each wave, there is a 1-2 month enrollment period. We anticipate approximately 80% of those screened will enroll, requiring approximately 110 individuals to be screened.

Potential participants will be identified by reviewing the clinic registries and/or EHR data using diagnostic codes for CP (ICD-10 G80-83), which contain detailed information about children and their diagnoses. We will send an “opt-out” letter that alerts families that a research study is being conducted and their child may be eligible, with a contact number to call if they wish to opt out of the research or if they wish to receive additional information or have any questions. Potentially eligible caregivers will be contacted by phone to screen for eligibility and interest.

If the research team is not notified that a family wishes to opt-out the research, the study research personnel will attempt to call the families (or meet them at an upcoming visit) to complete screening, informed consent, baseline questionnaires and random group assignment. Eligibility criteria for caregivers are detailed in **Study Population, Section 5.1-5.2**, and include being self-identified English- or Spanish-speaking caregivers of children with severe CP who have respiratory needs. CP status and additional eligibility criteria will be determined with a reliable and valid parent questionnaire and screener conducted at the beginning of initial phone contact.

Retention and Incentives

Study participants in this pilot RCT will be contacted at baseline (enrollment), monthly (for intervention subjects), and at 6 months (intervention and control groups). While we expect some degree of attrition will be inevitable, we will work to minimize attrition by sending regular follow-up post cards and phone calls requesting updates in contact information and also confirming or updating contact information when child medical records are reviewed. Moreover, participants will receive \$100 on study entry and exit.

Inclusion of Women and Minorities

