Just-in-time Adaptive Coaching Intervention Response. Coaching is accomplished by adapting PACT, which was initially adapted from the Care Transitions Intervention® (CTI),⁵⁰ to the pediatric population. The focus is: (1) medication self-management, (2) patient-centered records maintained by families, (3) timely follow-up, and (4) "red flags" and instructions how to identify/respond to them (i.e., action plans). Face-to-face visits are typically at the family's home; however, a neutral or "virtual" (telephone) visit is an option. Coaches review the four components, elicit goals, and focus coaching activities on needs identified by families. Phone calls discuss progress toward goals. This coaching approach provides the structure for JITAI activities.

Control Group. Those participants randomized to the control group will be provided usual care through the comprehensive clinical program at their children's hospital. They will also complete pre- and post-study assessments.

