Caregiver Strain	Survey	Caregiver Strain Questionnaire (CGSQ); ¹¹⁵ – mean global, objective, subjective scale scores Mental health (PHQ2) ¹¹⁶
Theory / Mechanism		
Capability	Survey	Family Caregiver Activation in Transition Measure (FCAT) ¹¹⁷ – mean composite score Caregiver General Self-Efficacy Scale (GSES) ¹¹⁸ – mean composite score
Opportunity	Survey	Family Experiences with Care Coordination (FECC) ¹¹⁹ - % top-box score for selected items
Motivation	Text logs	Confidence Responses mHealth texting (weekly score 1 through 10)

Assessment Procedures. Feasibility, acceptability and fidelity endpoint data will be collected during each of the three waves by research personnel reviewing study logs, conducting monthly chart reviews, and

administering surveys (by telephone, in person, or sending electronic self-administered links) with caregivers randomized to intervention. For active control groups participants, feasibility of assessments will be evaluated by completion rates at study exit. Caregiver and child measures above will be recorded at baseline, endpoints will be recorded at study exit (6 months after T0). Caregiving measures, which may change as a result of the intervention, will be collected at baseline and study exit. In addition, intervention and active control caregivers will be debriefed at study exit on their experiences in the study, and asked for feedback on the strengths, weaknesses and any concerns about the protocol. Between each wave and after the third wave, clinical teams at each site will be debriefed on strengths, weaknesses, and concerns about the protocol.

Reliability of Assessment Measures. The CP GMFCS measures and all the caregiving measures have been well-documented as reliable in the literature.^{11,74,115-119} We have separately established the reliability of identifying respiratory illnesses in our preliminary research (Kappa > 0.9). We will ensure reliability in data collection through direct observation, data auditing, establishing clear data dictionaries / definitions, using uniform variable definitions, and a central data repository coordinated and maintained by UW.

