9.1 STATISTICAL HYPOTHESES

- Primary Feasibility, Acceptability, Fidelity Endpoint(s): RE-PACT's primary outcomes will be analyzed descriptively, and evaluate feasibility, acceptability, fidelity using multiple approaches. Each outcome will be

assessed against our pre-specified measures of success, e.g., achieving at least 80% enrollment. By conducting iterative refinements over three waves of implementation, we expect to achieve success in all measures. We will assess all participant feedback using both quantitative and qualitative data to determine what study design changes would enhance a large-scale RCT. We will use inductive content analysis of qualitative data.

- Secondary Efficacy Endpoint(s): **To inform a future large multisite RCT, we will test** differences between treatment (I or AC) groups in the primary and secondary respiratory illness outcomes. Our goal with these analyses is to estimate effect sizes for the differences between groups. The primary clinical outcome is severe respiratory illness rate, defined as the total number of severe respiratory illnesses divided by the person-months over the 6 months period. The severe respiratory illness rate will be analyzed with negative binomial (NB) regression models to account for overdispersion in the count data. In the primary analysis, univariate NB regression analysis will be conducted with study arm as a predictor variable. Study site will be a stratification factor to account for stratified randomization. The observed effect size of the analysis will be quantified in terms of relative risk (RR) and reported along with the corresponding 95% confidence interval. A generalized linear mixed effects model with a logit link function and subject specific random effects will evaluate **longitudinal changes** in the severe respiratory illnesses within and between study arms. An autoregressive (AR) correlation structure will account for within subject correlations. In this analysis, presence/absence of severe respiratory illness at the monthly assessments will be the dependent variable; study arm will be included as a predictor variable, and study site as a stratification variable to account for the stratified randomization. **To investigate theoretical mechanisms**, we will test the mediating effect of caregiver capability, opportunity, and motivation (COM-B)¹¹³ measures on the relationship between intervention and respiratory exacerbations.

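### The longitudinal models compare arms on monthly outcomes, but the schedule gives monthly assessments to the intervention arm only, and no rule says how control-arm months are filled

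*Combined protocol and SAP*

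**What the plan says.** **Analysis.** Section 9.1 plans a mixed logistic model in which "presence/absence of severe respiratory illness at the monthly assessments will be the dependent variable". Section 9.4.3 repeats this and adds that "the presence/absence of severe respiratory illness at the monthly assessments will be the dependent variable, study arm will be included as a predictor variable". The same section extends the approach to steroid courses, antibiotic courses and emergency visits: "respiratory ED visits will be documented at the monthly assessments and longitudinal changes within and between study arms" are to be analyzed. The hospital-days model has a mixture component "to capture the probabilities of a hospitalization at the monthly follow-up". Missed monthly visits are listed among the missing values, to be examined by complete-case analysis and multiple imputation.

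**Collection.**
- Schedule (1.3): the row for monthly study assessments, T1 to T6, stands in the block headed "Intervention Arm Only".
- Section 5.5: after baseline, participants are contacted "monthly (for intervention subjects), and at 6 months (intervention and control groups").
- Section 6.1.1, on controls, after stating that they receive usual care: "They will also complete pre- and post-study assessments".
- Section 8.1: "endpoints will be recorded at study exit (6 months after T0"), with no limit by arm.
- Section 4.1: both groups have clinical measures taken by questionnaire and medical record review at baseline and 6 months.
- Synopsis (1.1): clinical outcomes are assessed at baseline and monthly for 6 months, with no limit by arm.

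**The concern.** A between-arm longitudinal model needs the same dependent variable, obtained in the same way, in both arms. Here the variable is tied to an assessment that the schedule, the retention text and the control-group description give to one arm.

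The assessment reads as a contact, not as a calendar rule. Section 8.3.4 has staff or a caregiver questionnaire ask at each monthly assessment about adverse events since the previous one, and 9.4.3 treats a missed monthly visit as missing data. If that is the source of the outcome, controls have no monthly rows. Complete-case analysis would then have nothing to compare, and imputation would have no observed control month to learn from. If control months are instead filled from an exit review while intervention months come from monthly contact, ascertainment differs by arm.

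The stake is limited but real. These are supplementary analyses of secondary outcomes in a pilot that the protocol expects to be underpowered, but section 9.4.3 says its between-arm effect sizes are meant to support sample size calculations for the next trial.

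**Working it through.** The plan states no figure on this point, so there is none to reproduce. The check is a comparison of sections, followed by arithmetic on scale.

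**1. Sections side by side**

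| Section | Monthly, intervention | Monthly, control | 6 months, both arms |
|---|---|---|---|
| 9.1, 9.4.3 (models) | needed | needed | – |
| 1.3 (schedule) | yes | not listed | yes |
| 5.5 (contacts) | yes | no | yes |
| 6.1.1 (control group) | – | before and after only | – |
| 1.1 (synopsis) | no arm named | no arm named | yes |
| 4.1 (clinical measures) | – | – | record review and questionnaire |
| 8.1 (endpoints) | – | – | at study exit |

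Two other mentions do not settle it. The monthly chart reviews in 8.1 concern feasibility, acceptability and fidelity data, which 4.1 collects monthly during the intervention but at 6 months for controls. The monthly study calls in 6.5 name no arm and concern action plans.

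**2. Scheduled assessments.** Inputs: 45 per arm (9.2) and six months.
- Intervention: 45 x 6 = 270. Control: 0 of 270.
- With 90% of participants retained (9.2): 0.9 x 270 = 243 child-months per arm.
- If control data were one exit record not split by month, there would be 45 control rows.

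These are scheduled contacts, not outcomes that cannot be obtained.

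**3. Events involved.** Inputs from 9.2: one severe illness per child-year and dispersion 1.0. A constant monthly rate is assumed.
- Expected control admissions: 45 x 1 x 0.5 = 22.5.
- Monthly mean: 1/12 = 0.0833.
- Chance of at least one in a month, negative binomial: 1 - 1/(1 + 1/12) = 0.0769, so 270 x 0.0769 = 20.8 child-months with an event.
- Poisson: 1 - exp(-1/12) = 0.0800, so 270 x 0.0800 = 21.6.
- At 243 child-months: 18.7 to 19.4.

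The control side of the model therefore rests on about 19 to 22 child-months with an event, and a few events missed or put in the wrong month would matter.

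**4. Illustration of unequal capture.** Suppose there is no true effect, capture is full in the intervention arm and a share s of control events is captured. The monthly probability is p(s) = 1 - exp(-s/12), and the apparent intervention/control odds ratio is [p(1)/(1 - p(1))] / [p(s)/(1 - p(s))].

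| s (assumed) | 1.00 | 0.95 | 0.90 | 0.80 | 0.70 |
|---|---|---|---|---|---|
| Apparent odds ratio | 1.00 | 1.05 | 1.12 | 1.26 | 1.45 |

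The documents give no capture rate for either arm. The table shows sensitivity to one assumed pattern and does not predict a bias.

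**The case against.** The strongest reply is that the data for both arms are already planned. Section 4.1 names record review and questionnaire in both groups at 6 months, 8.1 records endpoints at exit, and the main outcome is a hospitalization with a listed discharge diagnosis, which a chart can date. The synopsis gives monthly clinical outcomes without an arm limit. The loss-to-follow-up rule (7.3) also speaks of monthly assessments for any participant. On this view the schedule is merely inconsistent. The primary clinical analysis, the 6-month negative binomial rate, is untouched, and 9.4.1 refers to a detailed SAP, not included here as a separate text, that may contain the derivation.

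Most of this stands, and it rules out three stronger readings that a reader might infer:

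- *That the plan has no common source or follow-up period.* It has both: 4.1 and 8.1 as above, and a 6-month follow-up period in 9.4.3.
- *That outcome windows start at different times by arm*, because 6.1.1 attaches the T0 label to intervention activities within a month of enrollment. The synopsis equates baseline with randomization, 1.3 places randomization at the T0 enrollment visit, and no section starts an outcome window at intervention onset.
- *That control months cannot be obtained, or that bias runs in a known direction.* Dated records could supply those months, and unequal capture is possible but not shown.

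The reply does not remove the conflict. The models name the monthly assessment as their source, and three sections confine it to the intervention arm. The synopsis contradicts those sections without explaining how control months would be obtained. No section says that monthly outcomes are rebuilt from the exit review, which source decides, or how a month is bounded.

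**Conclusion.** The point holds as an internal conflict together with an unstated derivation rule, and it should be fixed. Followed literally, the longitudinal models have 270 scheduled monthly assessments in one arm and none in the other, or outcomes ascertained differently by arm. At the plan's own event rate, about 19 to 22 control child-months with a severe illness depend on the missing rule, assuming a constant monthly rate and 90% to 100% follow-up. The size and direction of any bias are unknown.

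The scope is limited to the longitudinal models for severe illness, steroid courses, antibiotic courses, emergency visits and hospital days. The descriptive primary endpoints and the 6-month rate analysis do not depend on monthly visits. Confidence is high that the sections conflict. It is lower that the rule is missing altogether, because the separate SAP was not available to check.

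**What to change.** In 8.1 and 9.4.3, and in the separate SAP before it is finalized:

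1. Replace the reference to monthly assessments or monthly follow-up with six monthly intervals counted from randomization.
2. Fill the intervals in both arms from dated admissions, emergency visits, and steroid and antibiotic courses taken from the sources already planned in both arms at 6 months. This means record review, with the exit questionnaire added only if it is used identically in both arms.
3. Do not let monthly contacts made only in the intervention arm define outcomes in any arm comparison.
4. Use the same events for the negative binomial totals, so that the two analyses agree.
5. Treat a month as missing only if the common sources do not cover it.
6. Reconcile 1.1, 1.3, 5.5, 6.1.1, 8.1, 9.1 and 9.4.3.

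The cost is wording plus date abstraction: about 45 admissions in total if rates are equal (2 x 22.5), and also emergency visits and drug courses. No new visits are needed. One small loss is that events known only from intervention-arm monthly reports would not count in the arm comparison.
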